## **F 3        Highly Effective Methods of Contraception**

Highly effective methods of contraception, defined as one that results in a low failure rate (ie, less than 1% per year) when used consistently and correctly, are described in [Table F11](#). Note that some contraception methods are not considered highly effective (eg, male or female condom with or without spermicide; female cap, diaphragm, or sponge with or without spermicide; non copper containing intrauterine device; progestogen-only oral hormonal contraceptive pills where inhibition of ovulation is not the primary mode of action [excluding Cerazette/desogestrel which is considered highly effective]; and triphasic combined oral contraceptive pills).

**Table F11      Highly Effective Methods of Contraception (< 1% Failure Rate)**

[figure not shown]
Non-hormonal methods	Hormonal methods

 
• Total sexual abstinence (evaluate in relation to the duration of the clinical study and the preferred and usual lifestyle choice of the participant)
 
• Vasectomised sexual partner (with participant assurance that partner received post-vasectomy confirmation of azoospermia)
 
• Bilateral tubal occlusion
 
• Intrauterine device (provided coils are copperbanded)
 
	
 
• Injection: Medroxyprogesterone injection (eg, Depo-Provera®) a
 
• Levonorgestrel-releasing intrauterine system (eg, Mirena®) a
 
• Implants: Etonogestrel-releasing implants (eg, Implanon® or Norplant®)
 
• Intravaginal devices: Ethinylestradiol/etonogestrel-releasing intravaginal devices (eg, NuvaRing®)
 
• Combined pill: Normal and low dose combined oral contraceptive pill
 
• Patch: Norelgestromin/ethinylestradiol-releasing transdermal system (eg, Ortho Evra®)
 
• Mini pill: Progesterone based oral contraceptive pill using desogestrel: Cerazette® is currently the only highly effective progesterone-based pill
 

a Hormonal methods not prone to drug-drug interactions.

## Appendix G Patient-reported Outcomes

### G 1 PAINS-pNF

CCI

CCI

CCI

CCI

CCI

CCI

[figure not shown]
CCI

CCI

CCI

CCI

[figure not shown]
CCI

■

[figure not shown]
CCI

[figure not shown]
CCI

CCI

[figure not shown]

CCI

**G 2      PII-pNF**

[figure not shown]
CCI

[figure not shown]
CCI

CCI

[figure not shown]
CCI

[figure not shown]
CCI

[figure not shown]
CCI

[figure not shown]
CCI

[figure not shown]
CCI

[figure not shown]
CCI

[figure not shown]
CCI

[figure not shown]
CCI

CCI

CCI

[figure not shown]

**G 3                    PROMIS**

CCI

[figure not shown]
**G 4      PlexiQoL**

[figure not shown]
CCI

[figure not shown]
CCI

CCI

[figure not shown]

CCI

**G 5      PedsQL NF1 Module Acute Version 3.0-Adult Report (Skin  
Sensations Domain)**

CCI

**G 6      PGIC**

***Patient Global Impression Of Change (1)***

Overall, how would you rate the change in your plexiform neurofibroma related chronic pain since  
your last visit to the study site?

- Much better
- Moderately better
- A little better
- About the same/No change
- A little worse
- Moderately worse
- Much worse

Overall, how would you rate the change in your plexiform neurofibroma related spikes of pain since  
your last visit to the study site?

- Much better
- Moderately better
- A little better
- About the same
- A little worse
- Moderately worse
- Much worse

### **Patient Global Impression Of Change (2)**

Overall, how would you rate the change in your plexiform neurofibroma related chronic pain since starting the study medication?

- Much better
- Moderately better
- A little better
- About the same/No change
- A little worse
- Moderately worse
- Much worse

Overall, how would you rate the change in your plexiform neurofibroma related spikes of pain since starting the study medication?

- Much better
- Moderately better
- A little better
- About the same
- A little worse
- Moderately worse
- Much worse

## G 7 PGIS

### ***Patient Global Impression Of Severity***

You have answered daily diary questions about a plexiform neurofibroma tumour that was selected by your doctor. Please think about **this area of your body** when answering the following questions.

Please select the response below that best describes the severity of your plexiform neurofibroma-related chronic pain over the past 7 days.

[figure not shown]
- No pain
- Mild
- Moderate
- Severe

Please select the response below that best describes the severity of your plexiform neurofibroma related spikes of pain over the past 7 days.

[figure not shown]
- No pain
- Mild
- Moderate
- Severe

**G 8      EQ-5D-5L Health Questionnaire**

CCI

[figure not shown]

CCI

[figure not shown]
## Appendix H Guidance for Management of Specific Adverse Events

### H 1 Management of Left Ventricular Ejection Fraction (LVEF) Reduction (asymptomatic) or Left Ventricular Systolic Dysfunction (LVSD)

[figure not shown]
ECHO, echocardiogram; LLN, lower limit of normal, LVEF, left ventricular ejection fraction; LVSD, left ventricular systolic dysfunction.

## H 2 Management of Creatine Kinase (CK) Elevation

[figure not shown]
CK, creatine kinase; CTC Common Terminology Criteria; ULN, Upper Limit of Normal.

### H 3 Management of Retinal Pigment Epithelial Detachment (RPED), Central Serous Retinopathy (CSR) and Retinal Vein Occlusion (RVO)

[figure not shown]
CSR, central serous retinopathy; RPED, retinal pigment epithelial detachment; RVO, retinal vein occlusion

## H 4 Management of Diarrhoea

CTC, Common Terminology Criteria

[figure not shown]
## H 5 Management of New or Worsening Dyspnoea

[figure not shown]
BNP, brain natriuretic peptide; CT, computed tomography; ECG, electrocardiogram; Hb, haemoglobin; ILD, interstitial lung disease; P-A, posterior-anterior; WBC, white blood cell

## H 6 Management of Participants with Rash

### H 6.1 Management of Rash

[figure not shown]
### H 6.2 Rash: Adult Treatment Recommendations

## **H 7        Oral Care Management for Events of Oral Mucositis and Dry Mouth**

- Participants should be encouraged to follow a daily oral health care regimes, both before and during treatment with selumetinib.
- Participants with a healthy mouth may use non-alcoholic mouthwash 4 to 6 times daily (eg, after each meal), or according to the instructions, during the study.
- Saline mouthwashes (sodium chloride 0.9%) are preferred to alcohol-based mouth washes in cases of stomatitis, and should be used at a different time than tooth brushing (eg, after tea).
- Use of a mouthwash immediately after selumetinib intake is recommended.
- The tongue can be gently brushed (if not sore) with a soft toothbrush.
- Participants with, or at risk of, stomatitis should not use commercial/over-the-counter mouthwashes because of the alcohol content and astringency. Chlorhexidine mouthwashes are not recommended for the treatment of established stomatitis.
- The mouth should be regularly inspected by the participant and healthcare professionals.
- Teeth should be brushed twice daily with a fluoride toothpaste and soft toothbrush, in the morning before breakfast and last thing in the evening before bed, about 30 minutes after eating. The toothbrush should be replaced regularly (at least every 3 months). Participants with stomatitis should change their toothbrush every 4 to 6 weeks.
- Consider culture to rule out herpes simplex.
- Consider treating stomatitis at an early stage (CTCAE Grade 1) or as soon as the participant complains of a sore mouth. Consider using an oral topical analgesic, with or without topical steroids, depending on the participant's clinical condition and the local standard medical practice.

## H 8 Management of Paronychia

CTC, Common Terminology Criteria

**Table H12 Treatment Recommendations for AE Paronychia a**

Severity	Treatment Recommendations
CTCAE Grade 1	Treat the affected area by soaking in vinegar solution twice daily (1 part vinegar to 2 parts water) and topical antibiotic mupirocin twice daily.
CTCAE Grade 2	Treat the affected area by soaking in vinegar solution twice daily (1 part vinegar to 2 parts water) and systemic antibiotic (Keflex, Clindamycin) and high potency steroid (0.05% clobetasol ointment covered with saran wrap OR flurandrenolide tape [Cordran tape]) applied at bedtime. This should be removed in morning.
CTCAE Grade 3	If severe, seek consult for incision and drainage or surgical management.

a If granulation tissue present, consider use of silver nitrate under supervision.

AE, adverse event; CTCAE, Common Terminology Criteria for Adverse Events

For participants who do not undergo drainage, silver nitrate may be used, as well as topical bactroban, steroids, and/or antifungals. Silver nitrate is only of value when there is open inflamed skin or granulation tissue (eg, pyogenic-granuloma-like lesions). If the periungual skin is swollen but intact (whether infectious or non-infectious), silver nitrate is not recommended.

Participants should be cautioned to avoid trauma to the area. Podiatry consult may be considered for partial nail removal.

Participants who undergo incision and drainage and are found to have no infectious organisms on culture, should be treated as above. If infection is identified, participants may be treated with systemic antibiotics (oral tetracyclines).

If paronychia recurs or develops in other fingers or toes, flurandrenolide (eg, Cordran) tape or topical steroid cream such as triamcinolone can be used in the morning and Bactroban and Nizoral topical ointments in the evening.

## Appendix I Cardiovascular Grading

**Table I13 Canadian Cardiovascular Society Grading of Angina Pectoris**

Grade	Description
I	Ordinary physical activity does not cause angina, such as walking and climbing stairs. Angina with strenuous or rapid or prolonged exertion at work or recreation.
II	Slight limitation of ordinary activity. Walking or climbing stairs rapidly, walking uphill, walking or stair climbing after meals, or in cold, or in wind, or under emotional stress, or only during the few hours after awakening. Walking more than two blocks on the level and climbing more than one flight of ordinary stairs at a normal pace and in normal conditions.
III	Marked limitation of ordinary physical activity. Walking one or two blocks on the level and climbing one flight of stairs in normal conditions and at normal pace.
IV	Inability to carry on any physical activity without discomfort, anginal syndrome may be present at rest.

**Table I14 New York Heart Association Classification**

New York Heart Association grading	Metabolic equivalent a
Class I	No limitations. Ordinary physical activity does not cause undue fatigue, dyspnoea or palpitations (asymptomatic left ventricular dysfunction).
Class II	Slight limitation of physical activity. Ordinary physical activity results in fatigue, palpitation, dyspnoea or angina pectoris (mild congestive heart failure).
Class III	Marked limitation of physical activity. Less than ordinary physical activity leads to symptoms (moderate congestive heart failure).
Class IV	Unable to carry on any physical activity without discomfort. Symptoms of congestive heart failure present at rest (severe congestive heart failure).

a Metabolic equivalent is defined as the resting  $\text{VO}_2$  for a 40-year-old 70 kg man. Metabolic equivalent = 3.5 mL  $\text{O}_2$ /min/kg body weight.  
 $\text{VO}_2$ , maximal oxygen uptake.

## Appendix J Concomitant Medications

### J 1 Guidance Regarding Potential Interactions with Concomitant Medications

Throughout the study, participants should avoid changes to, or the addition of, all concomitant medications and, in particular, any that may affect the metabolism of selumetinib (eg, CYP2C19 or CYP3A4 moderate/strong inhibitors, as well as CYP3A4 moderate/strong inducers), unless considered clinically indicated. The use of any natural/herbal products or other “folk remedies” should be discouraged, but use of these products, as well as use of all vitamins, nutritional supplements, and all other concomitant medications must be recorded in the eCRF.

Strong or moderate **inducers** of CYP3A4 are not allowed at any time during the study. During the first cycle concomitant use of **strong or moderate inhibitors of CYP3A4 or CYP2C19**, with the exception of chronic PN pain medication, should be avoided until after the PK assessment. During the remainder of the study, if concomitant use of selumetinib with strong or moderate CYP3A4 or CYP2C19 inhibitors is not avoidable, then the selumetinib dose should be reduced as shown in [Table J15](#). For chronic PN pain medication fulfilling the above criteria, selumetinib should be initiated at a reduced dose as shown in [Table J15](#). The dose of selumetinib should be reduced for the duration of concomitant therapy with the strong or moderate CYP3A4 or CYP2C19 inhibitor and for 5 half-lives afterwards. After the washout of the inhibitor is complete, the selumetinib dose can be re-escalated. The participant should be monitored closely for potential toxicities.

In vitro, selumetinib is an inhibitor of OAT3. The potential for a clinically relevant effect on the PK of concomitantly administered substrates of OAT3 (eg, methotrexate, furosemide benzylpenicillin, baricitinib and tenofovir) cannot be excluded and they should be administered with caution.

**Table J15 Recommended Dosage of Selumetinib for Co-administration with Strong or Moderate CYP2C19 or CYP3A4 Inhibitors**

BSA (m  )	If the current dosage is up to 25 mg/m  bid, reduce to 20 mg/m  bid		If the current dosage is up to 20 mg/m  bid, reduce to 15 mg/m  bid	
	AM	PM	AM	PM
1.10 – 1.29	25	25	25	10
1.30 – 1.49	30	25	25	20
1.50 – 1.69	35	30	25	25
1.70 – 1.89	35	35	30	25
≥ 1.90	40	40	30	30

bid, twice daily; BSA, body surface area; CYP, cytochrome P450.

Changes to, or addition of medications detailed in [Table J16](#) and [Table J17](#) should be avoided, unless clinically indicated. The lists in [Table J16](#) and [Table J17](#) are not intended to be exhaustive, and a similar restriction will apply to other agents that are known to affect CYP2C19, or CYP3A4 activity. Appropriate medical judgment is required. Please contact AstraZeneca with any queries.

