## 6.5 Concomitant Therapy

Any concomitant treatment, procedure, or other medication considered necessary by the investigator for the participant's safety and wellbeing, or vaccine (including over-the-counter or prescription medicines, vitamins, and/or herbal supplements) that the participant is receiving from the time of screening or receives during the study including the 30 day follow-up period following the last dose of study intervention must be recorded in the eCRF along with:

- Reason for use.
- Dates of administration including start and end dates.
- Dosage information including dose and frequency.

The AstraZeneca Medical Monitor should be contacted if there are any questions regarding concomitant or prior therapy.

If any concomitant therapy is administered due to new or unresolved AE, it should be recorded.

Participants must be instructed not to take any medications, including over-the-counter products, without first consulting with the investigator.

Strong or moderate **inducers** of **CYP3A4** are not allowed at any time during the study. During the first cycle, concomitant use of strong or moderate **inhibitors of CYP3A4 or CYP2C19**, with the exception of chronic PN medication, should be avoided until after the PK assessment. If concomitant use of selumetinib with strong or moderate CYP3A4 or CYP2C19 inhibitors is not avoidable, then the selumetinib dose should be reduced as shown in [Appendix J Table J15](#). For chronic PN pain medication fulfilling the above criteria, selumetinib should be initiated at a reduced dose as shown in [Appendix J Table J15](#). The dose of selumetinib should be reduced for the duration of concomitant therapy with the strong or moderate CYP3A4 or CYP2C19 inhibitors and for 5 half-lives afterwards. After the washout of the inhibitor is complete, the selumetinib dose can be re-escalated. The participant should be monitored closely for potential toxicities.

In vitro, selumetinib is an inhibitor of OAT3. The potential for a clinically relevant effect on the PK of concomitantly administered substrates of OAT3 cannot be excluded and they should be administered with caution.

Selumetinib capsules contain vitamin E in the form of D- $\alpha$ -tocopheryl polyethylene glycol

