## 6.6 Dose Modification

Specific guidance for the management of AEs, including interruption or reduction of treatment with selumetinib, may be considered for particular events of special interest (eg, diarrhoea, dyspnoea, rash, asymptomatic reduction in LVEF, and visual disturbance), as indicated in the algorithms provided in [Appendix H](#).

For all AEs reported in this study that are considered at least partly related to administration of selumetinib, the following dose reduction/adjustment guidance should be applied unless otherwise specified in the guidance for management of specific AEs ([Appendix H](#)):

Treatment with selumetinib should be temporarily interrupted if one of the following AEs occurs and is considered related to treatment with selumetinib:

- Any intolerable AE regardless of grade.
- Any AE CTCAE Grade  $\geq 3$ .

On improvement of the AE to CTCAE Grade 1 or less within 4 weeks of onset, study intervention may be restarted at the discretion of the investigator. If restarted, it must be at a reduced dose as shown in [Table 7](#). If the AE does not resolve to CTCAE Grade 1 or less within 4 weeks of onset, study intervention must be permanently discontinued unless otherwise specified in the Guidance for Management of Specific AEs ([Appendix H](#)).

The dose modification procedure is shown in [Table 7](#). Two step dose modification is applied in the study. Any participants with 2 prior dose reductions who experience a toxicity that would cause a third dose reduction must be discontinued from study intervention.

Dose must not be re-escalated following dose reduction apart from to account for increase due to BSA, in accordance with [Table 7](#). For example, if a participant has a BSA of  $1.8 \text{ m}^2$  and starts on a dose of 45 mg bid and then has a dose reduction to 35 mg AM, 30 mg PM then a

subsequent BSA increase to 1.9 m^2 would mean the participant should be dose adjusted to 35 mg bid.

Note that if selumetinib is interrupted for more than 4 weeks for any reason other than AEs related to selumetinib eg, investigations, unplanned procedures and AEs unrelated to selumetinib, re-start of treatment must be discussed with the AstraZeneca Medical Monitor.

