**Table 7 Dose Modification Procedure**

Body surface area (m^2)	Selumetinib starting dose (mg) a		First selumetinib dose (mg) reduction		Second selumetinib dose (mg) reduction	
	AM	PM	AM	PM	AM	PM
1.1. to 1.29	30	30	25	20	20	10
1.3 to 1.49	35	35	25	25	25	10
1.5 to 1.69	40	40	30	30	25	20
1.7 to 1.89	45	45	35	30	25	20
≥ 1.90	50	50	35	35	25	25

a Actual dose in mg (capsule sizes 10 and 25 mg) administered every 12 hours to achieve a dosage of 25 mg/m^2 bid, twice daily.

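### Table J15 gives participants at the second toxicity reduction a higher daily dose, not a lower one, when a CYP2C19 or CYP3A4 inhibitor is added

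*Protocol*

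**What the plan says.** Table 7 (Section 6.6) sets two toxicity steps by BSA band, headed "First selumetinib dose (mg) reduction" and "Second selumetinib dose (mg) reduction". Participants may stay on treatment at the second step: "Any participants with 2 prior dose reductions who experience a toxicity that would cause a third dose reduction must be discontinued from study intervention". Section 6.6 also states: "Dose must not be re-escalated following dose reduction apart from to account for increase due to BSA".

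When a strong or moderate CYP3A4 or CYP2C19 inhibitor is unavoidable, Section 6.5, Appendix J 1 and Table J18 all send the site to Table J15 for a reduced dose. J15 has two pairs of columns. The upper pair is for a current dosage of up to 25 mg/m² bid and reduces it to 20. The header of the lower pair begins "If the current dosage is up to 20 mg/m"² bid and reduces the dosage to 15. Neither header has a lower bound.

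On stopping the inhibitor, Section 6.5 says: "After the washout of the inhibitor is complete, the selumetinib dose can be re-escalated". It does not say to what level. The general fallback is that "The AstraZeneca Medical Monitor should be contacted if there are any questions regarding concomitant or prior therapy". The text below Table J15 likewise calls for medical judgment and contact with the sponsor.

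**The concern.** A participant at the second Table 7 reduction has already needed two dose cuts for toxicity. The current dose is well below 20 mg/m², so the lower J15 columns appear to apply, yet the doses printed there are set for a target of 15 mg/m² bid. If the second reduction is already at or below that level, following the table raises the dose just as an exposure-raising inhibitor is added. That contradicts the instruction to reduce and the Section 6.6 bar on re-escalation.

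This is a safety rule. For these participants, the next toxicity that would call for a reduction means discontinuation. A table that points the wrong way, or to nothing, leaves the site to improvise.

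**Working it through.** **Inputs.** AM and PM doses in mg from Table 7 and Table J15. Daily total = AM + PM. Dose per m² per administration = daily total ÷ 2 ÷ BSA, at the limits of each band.

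**Reproducing J15.** A target of 15 mg/m² bid at the band midpoint (1.90 m² for the open top band) is 15 × 2 × BSA = 35.9, 41.9, 47.9, 53.9 and 57.0 mg/day. The table gives 35, 45, 50, 55 and 60. These agree to within about 3 mg, which is reasonable with 10 mg and 25 mg capsules. J15 is not miscalculated for its own target.

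**Daily totals (mg/day).**

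| BSA (m²) | Table 7 start | Table 7 first reduction | Table 7 second reduction | J15 upper | J15 lower | J15 lower minus second reduction |
|---|---|---|---|---|---|---|
| 1.10–1.29 | 60 | 45 | 30 | 50 | 35 | +5 (+16.7%) |
| 1.30–1.49 | 70 | 50 | 35 | 55 | 45 | +10 (+28.6%) |
| 1.50–1.69 | 80 | 60 | 45 | 65 | 50 | +5 (+11.1%) |
| 1.70–1.89 | 90 | 65 | 45 | 70 | 55 | +10 (+22.2%) |
| ≥ 1.90 | 100 | 70 | 50 | 80 | 60 | +10 (+20.0%) |

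**Cell by cell, J15 lower against second reduction.** AM: 25 v 20, 25 v 25, 25 v 25, 30 v 25, 30 v 25. PM: 10 v 10, 20 v 10, 25 v 20, 25 v 20, 30 v 25. Seven cells are higher, three are equal and none is lower.

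**Does the lower pair of columns apply?** The second reduction per administration is:
- 15/1.29 to 15/1.10 = 11.6 to 13.6 mg/m²
- 17.5/1.49 to 17.5/1.30 = 11.7 to 13.5 mg/m²
- 22.5/1.69 to 22.5/1.50 = 13.3 to 15.0 mg/m²
- 22.5/1.89 to 22.5/1.70 = 11.9 to 13.2 mg/m²
- at most 25/1.90 = 13.2 mg/m² in the top band

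Every value is within up to 20 mg/m², and none exceeds the 15 mg/m² that J15 says to reduce to.

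**Where J15 works.** From the starting dose, the upper columns cut 10/15/15/20/20 mg/day. From the first reduction, the lower columns cut 10/5/10/10/10 mg/day (22.2%, 10.0%, 16.7%, 15.4%, 14.3%). There is one exception if the headers are read strictly in mg/m². The first reduction in the lowest band exceeds 20 mg/m² where 22.5/BSA > 20, that is, BSA below 1.125 m². The upper columns would then apply and give 50 instead of 45 mg/day (+11.1%).

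**Size against the starting dose.** J15 lower ÷ start = 35/60, 45/70, 50/80, 55/90 and 60/100 = 58% to 64%.

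**The case against.** The best counter-argument is that J15 is silent on these participants and does not direct an increase. Its header says to reduce, and 11.6 to 15.0 mg/m² cannot be reduced to 15. Section 6.6 is mandatory, whereas J15 is headed as a recommendation. The columns also look like nominal dose levels. The starting dose is 26.3 to 27.3 mg/m² at the lower limit of each band, yet the Table 7 footnote describes it as "administered every 12 hours to achieve a dosage of 25 mg/m"² bid. On that view J15 covers 25 to 20 and 20 to 15 only.

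This has force, but it does not repair the rule. On the ordinary meaning of up to, a second-reduction dose still sits under the lower header, and the row printed there is higher. If Section 6.6 prevails, it forbids that dose and gives no other. If the nominal reading prevails, the second reduction is outside the table and again has no dose.

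Several mitigating points stand. Exclusion criterion 18 keeps out inhibitors at entry unless they can be stopped, with an exception for chronic PN pain medication. Appendix J advises against adding inhibitors unless clinically indicated and asks for close monitoring. The Medical Monitor can be consulted. Section 6.6 requires stopping for a toxicity that would cause a third reduction, but it does not prohibit a lower dose for a drug interaction. These provisions lower the risk, but none names an action for this situation, and a site that finds an apparently applicable row may see nothing to ask about.

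The exception below 1.125 m² is marginal. By the Mosteller formula in Section 8.2.2, and assuming a height of 150 cm, a BSA of 1.12 m² means 1.12² × 3600/150, or about 30 kg, in an adult trial.

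**Conclusion.** The concern holds: the dosing rules are wrong as written for participants at the second Table 7 reduction. In all five BSA bands Table J15 gives them 5 to 10 mg/day more (11.1% to 28.6%), before any rise in exposure from the inhibitor. On the other reading they have no specified dose. J15 works from the starting dose and, apart from the marginal BSA exception, from the first reduction.

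The figures rest only on the two printed tables. The consequence is limited. It needs two toxicity reductions, continued treatment and an unavoidable inhibitor, so the group is probably small. The documents give neither a frequency nor an inhibitor exposure ratio, so the harm cannot be quantified, and a misapplied J15 dose would still be below the starting dose. No efficacy analysis depends on this. It should be fixed because it is a safety instruction for participants who have already shown intolerance.

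**What to change.** State in Table J15, with a cross-reference in Section 6.5, Appendix J 1 and Table J18:

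1. The dose given with a strong or moderate CYP3A4 or CYP2C19 inhibitor must never exceed the participant's current dose.
2. Where J15 gives no reduction, which includes every participant at the second Table 7 reduction, the action is to avoid the inhibitor, interrupt selumetinib, or use a sponsor-specified lower dose agreed with the Medical Monitor.
3. Re-escalation after inhibitor washout returns only to the pre-inhibitor dose and keeps any earlier toxicity reduction.

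The sponsor's clinicians should choose the action and any lower dose.

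The cost is a few sentences of protocol wording and a memo to sites, with no added participants, visits or procedures. A protocol amendment may need ethics committee and regulatory approval under Appendix A 1, so the change can go into the next planned amendment, with Medical Monitor guidance to sites until then.

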**Table J16      Inhibitors of CYP2C19 or CYP3A4 that AstraZeneca Recommends not to be Combined with Selumetinib**

CYP2C19	CYP3A4
Strong	Strong
Fluconazole	Indinavir
Fluvoxamine	Nelfinavir
Fluoxetine	Ritonavir
Ticlopidine	Saquinavir
Moderate	Cobicistat
(S)-omeprazole (esomeprazole) high dose 80 mg bid a	Telaprävir
stiripentol	Itraconazole
voriconazole	Ketoconazole
triclabendazole	Voriconazole
Cannabidiol b	Troleandomycin
fedratinib	Mifepristone
omeprazole	Clarithromycin
efavirenz	Lonafarnib
moclobemide	Posaconazole
	Grapefruit juice
	Conivaptan
	Tucatinib
	Ceritinib
	Nelfinavir
	Ribociclib
	Idelalisib
	Moderate
	Erythromycin
	Fluconazole
	Atazanavir
	Duvelisib
	Diltiazem

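### For a participant at the second Table 7 toxicity reduction, the lower column of Table J15 prints a dose 5 to 10 mg/day (11% to 29%) above the current one in every BSA band

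*Protocol*

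**What the plan says.** Appendix J 1 covers strong or moderate CYP3A4 or CYP2C19 inhibitors. If concomitant use with these "inhibitors is not avoidable, then the selumetinib dose should be reduced as shown in" Table J15. Section 6.5 gives the same instruction, and Table J18 repeats it. None of the three makes an exception for a participant already reduced for toxicity.

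Table J15 has two dose columns. The first is headed "If the current dosage is up to 25 mg/m 2 bid, reduce to 20 mg/m 2 bid" and the second "If the current dosage is up to 20 mg/m 2 bid, reduce to 15 mg/m 2 bid". There is no third column and no lower bound on the second.

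Toxicity reductions are set separately in Section 6.6. Table 7 has two steps, the last headed "Second selumetinib dose (mg) reduction". Section 6.6 adds: "Dose must not be re-escalated following dose reduction apart from to account for increase due to BSA". A toxicity that would call for a third reduction means permanent discontinuation. Section 6.6 does not mention Table J15.

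For the end of inhibitor use, Appendix J 1 states: "After the washout of the inhibitor is complete, the selumetinib dose can be re-escalated".

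**The concern.** The inhibitor rule exists to lower the selumetinib dose when another drug may raise its exposure. Table J15 appears to have been built for two situations: the starting dose, and a dose already reduced once. A participant who has been reduced twice is below both, yet the wording of the lower column still takes that participant in.

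At stake is the safety of a small group. These participants have already had two dose cuts for toxicity considered at least partly related to selumetinib, and one more such toxicity ends their treatment. A site using Table J15 as a plain look-up would raise the dose at the moment the inhibitor is started. A site that notices the conflict finds no dose in the protocol to use instead.

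**Working it through.** **Inputs.** AM and PM doses by BSA band come from Table 7 (Section 6.6) and Table J15 (Appendix J 1). The plan states no figure of its own to reproduce; the check is table arithmetic.

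**Step 1: does the lower column include this participant?** Current dosage in mg/m² bid = (AM + PM) / 2 / BSA, taken at the band limits:

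- BSA 1.10 to 1.29: 15/1.10 = 13.6 down to 15/1.29 = 11.6
- BSA 1.30 to 1.49: 17.5/1.30 = 13.5 down to 17.5/1.49 = 11.7
- BSA 1.50 to 1.69: 22.5/1.50 = 15.0 down to 22.5/1.69 = 13.3
- BSA 1.70 to 1.89: 22.5/1.70 = 13.2 down to 22.5/1.89 = 11.9
- BSA 1.90 and above: 25/1.90 = 13.2, and lower as BSA rises

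All are below 20, so the heading's condition is met. All are also at or below 15, the level the column is meant to reach.

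**Step 2: what dose does it print?** Daily dose = AM + PM. Percentage = (J15 − second reduction) / second reduction.

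| BSA (m²) | Table 7, second reduction (mg/day) | J15, 15 mg/m² column (mg/day) | Difference | Percentage |
|---|---|---|---|---|
| 1.10–1.29 | 20 + 10 = 30 | 25 + 10 = 35 | +5 | 5/30 = 16.7% |
| 1.30–1.49 | 25 + 10 = 35 | 25 + 20 = 45 | +10 | 10/35 = 28.6% |
| 1.50–1.69 | 25 + 20 = 45 | 25 + 25 = 50 | +5 | 5/45 = 11.1% |
| 1.70–1.89 | 25 + 20 = 45 | 30 + 25 = 55 | +10 | 10/45 = 22.2% |
| ≥ 1.90 | 25 + 25 = 50 | 30 + 30 = 60 | +10 | 10/50 = 20.0% |

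**Step 3: is the fault specific to this level?** From the starting dose, the 20 mg/m² column goes 60 to 50, 70 to 55, 80 to 65, 90 to 70 and 100 to 80 mg/day, a cut of 10 to 20 mg/day. From the first reduction, the 15 mg/m² column goes 45 to 35, 50 to 45, 60 to 50, 65 to 55 and 70 to 60 mg/day, a cut of 5 to 10 mg/day. Used step by step, the table does what it should at both levels. It fails only at the second reduction.

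**The case against.** The best reply is that no sentence tells a site to raise the dose. Both column headings say to reduce, the referring text says to reduce, and Section 6.6 forbids re-escalation except for a BSA increase. Section 6.5 tells sites to contact the Medical Monitor with questions about concomitant therapy, and the text below Table J15 adds "Appropriate medical judgment is required. Please contact AstraZeneca with any queries". Table J16 lists "Inhibitors of CYP2C19 or CYP3A4 that AstraZeneca Recommends not to be Combined with Selumetinib", and most such drugs are kept out at entry by exclusion criterion 18, apart from chronic PN pain medication. On a purposive reading, the two columns are steps and the second reduction simply falls outside the table.

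Much of this stands. A reader might infer that the protocol directs an increase, or that these participants will be overdosed; the documents do not support that. What remains is that the words of the lower column include the participant. None of the other texts says that the table does not apply at the second reduction, and none supplies a dose. If the table is read as silent instead, the site has an instruction to reduce and nothing to reduce to.

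Two further inferences should be resisted:

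- A reader might apply the upper column as well, since a dose under 20 is also under 25, and derive a larger increase. That reading would also raise every first-reduction participant (45 to 50, 50 to 55, 60 to 65, 65 to 70 and 70 to 80 mg/day), so it cannot be what the table means.
- A reader might take the washout sentence as permission to go back above the last toxicity-reduced level. The Section 6.6 ban most naturally caps that dose, and the sentence most naturally reverses only the inhibitor-related cut. It merits a clarifying phrase, not a finding of its own.

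**Conclusion.** Table J15 is wrong as written for one dose level. At the second Table 7 reduction, the only column that sensibly matches prints a dose 5 to 10 mg/day (11% to 29%) above the current one in all five BSA bands, against its own heading and against Section 6.6. The table should be corrected on grounds of participant safety.

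The arithmetic is certain. The practical consequence is less so. It needs two toxicity reductions, an unavoidable strong or moderate inhibitor, and a site that follows the cell rather than the surrounding text. The documents give neither the number of participants likely to be in this position nor the extra exposure an inhibitor would cause; the number is probably small. Any effect on the primary endpoint is remote, and nothing here supports a claim that the efficacy analyses are compromised. The conclusion assumes that current dosage means the dose being taken divided by BSA.

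**What to change.** Change Appendix J 1 as follows:

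1. Key the Table J15 columns to the Table 7 step: the 20 mg/m² column for participants with no Table 7 reduction, and the 15 mg/m² column for participants on the first reduction. This also removes a small edge case. At first reduction with BSA 1.10 to 1.12 the dosage is 22.5/1.10 = 20.5 down to 22.5/1.12 = 20.1 mg/m² bid, just over 20, so the present headings point to 50 mg/day for someone taking 45.
2. Add below the table: *Table J15 must never be used to set a dose above the participant's current dose; after inhibitor washout the dose returns to no higher than the last Table 7 level.* The second half only makes explicit what Section 6.6 already implies.
3. Add: *At the second Table 7 reduction, Table J15 does not apply; avoid the inhibitor, or if it is unavoidable contact the AstraZeneca Medical Monitor before co-administration.* This turns the general advice in Section 6.5 into a required step where it is needed.

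The cost is two column headings and two short notes. No participants, visits or data items are added, and the SAP does not change.
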